fractions or fewer is more immune-stimulatory, whereas a longer course of conventionally fractionated radiation is more immunosuppressive, through their differential effects on the up- and down-regulation of CD8 T-cells, Treg and MDSC cells, and expression of OX40, PD-L1, and MHC-1.²²⁻²⁴ Fractionated courses are also superior to a single fraction treatment in stimulating an abscopal effect.²² As such, for the purposes of this study, we will use a dose of 6-12Gy per fraction in 3 fractions (total dose 18-36 Gy) or 4-10 Gy per fraction in 5 fractions (total dose 20-50 Gy) to be completed over the course of 3-21 days. This variety of regimens offers a biologically effective dose (BED) range of 28-100 for early responding tissue (which correlates with tumor control) and 47-217 for late responding tissue (which correlates with side effects). This will give the treating physician a full range of options, such that an adequate dose can be given to the tumor while meeting all dose constraints of normal organs. The optimal hypofractionated radiation regimen is unknown, and there is some evidence that lower dose (and thus less ablative) regimens that would result in inferior local control may actually be more systemically immune-stimulating.²⁴ As such, regimens with a lower BED will be favored for this study, with the exception of situations in which improved local control to palliate symptoms is also a priority. Higher BED regimens may also be considered for larger size tumors and more rapidly growing tumors. This general preference for lower dose regimens will also have the favorable consequence of reducing the morbidity of therapy. Visceral metastases or metastases in organs involved in the immune system (e.g. liver) will be targeted preferentially over bone metastases due to the increased likelihood of an abscopal effect that has been previously reported for tumors in these sites.^{13-14, 25} If a bone metastasis requires treatment for palliative purposes we advise also treating a visceral metastasis concurrently. Brain metastases will be treated according to standard of care if they develop during the period of trial enrollment, but because there is little evidence to suggest that treating a brain metastasis can elicit an extracranial systemic response, we advise also treating a visceral metastasis concurrently to increase the likelihood of an abscopal effect.

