5.2. Standard of Care Immune Checkpoint Inhibitors

Immune checkpoint inhibitors that are FDA approved for use in patients with metastatic NSCLC will be acceptable for use concurrently with radiotherapy in this trial. The choice of agents will be at the treating medical oncologist's discretion, and include:

- Nivolumab 240 mg once every 2 weeks (14 day cycle) or 480 mg once every 4 weeks (28 day cycle)
- Pembrolizumab 200 mg once every 3 weeks (21 day cycle)
- Atezolizumab 1200 mg once every 3 weeks (21 day cycle)

These agents should be continued per standard of care until either disease progression or unacceptable toxicity. In the case of Pembrolizumab, it is also recommended that patients should be on the drug for no more than 24 months even if there is no evidence of disease progression. Pembrolizumab may also be used in combination with Pemetrexed and Carboplatin for the first-line treatment of metastatic non-squamous NSCLC. If any of the immune therapy agents are permanently discontinued at any point, a final course of radiation therapy should be offered to the patient before switching to an alternative therapy. While the patient is receiving immune therapy, no other investigational or commercial agents or therapies may be administered with the intent to treat the subject's malignancy.

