5.3. Subsequent Response-Adapted Radiation Therapy

Any patient who completes the initial course of radiation therapy and continues on one of the immune checkpoint inhibitors described above will be eligible for subsequent course(s) of radiation therapy to a different lesion that was not previously irradiated based on the results of follow-up imaging studies detailed below and in section 11.

- Patients with a partial or complete response per irRC criteria will be observed without any further radiation therapy until progression.
- Patients with stable disease per irRC criteria will undergo an additional course of radiation therapy given concurrently with the next cycle of immune checkpoint

- therapy, and then continue the immune therapy as above. Each subsequent course of radiation therapy should ideally be at least 2 months after completion of the prior course of radiation therapy, but is left at the discretion of the treating physician depending on the patient's palliative needs. Day 1 of radiation should be on Day 1 of the next cycle of immune therapy.
- Patients with progressive disease at any time per irRC criteria will undergo a final course of radiation therapy. This may be given concurrently with a final cycle of immune therapy or as stand-alone treatment within 6 weeks after discontinuation of immune therapy but before an alternative systemic therapy is initiated.

Please see Section 5.5 below regarding situations in which these subsequent courses of radiation therapy may be withheld. Each subsequent course of radiation therapy should be given in a similar style as detailed for the initial course of radiation therapy above. In patients with a mixed response to therapy, preference will be given to an enlarging tumor (rather than one that is stable or decreasing in size) as the site of treatment. Reimaging will again be obtained after completion of the radiation therapy with timing at the discretion of the treating physicians, and the same response-adapted approach to decision making for further courses of radiation therapy will be carried out as described above.

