⁶Serum chemistries include sodium, potassium, chloride, bicarbonate, BUN, creatinine, glucose, calcium, magnesium, phosphorous, albumin

⁷Serum liver function tests include alkaline phosphatase, total bilirubin, total protein, SGOT [AST], SGPT [ALT]

⁸Only for women of childbearing potential (within 14 days of registration)

⁹Only for patients with diabetes mellitus

¹⁰In patients with contrast allergy a short course of steroids may be given as needed. In patients with poor kidney function in whom contrast is contraindicated a non-contrast imaging study is permissible.

¹¹Please refer to protocol section 9 for details. The initial research blood sample may be drawn anytime between signing the consent and the first immune therapy treatment.

¹²Record all past and current administrations of immune therapy (sections 5.2 and 6.2), including date and dose of each administration.

¹³Record all past and current administrations of radiation therapy (sections 5.1, 5.3, and 6.1), including for each course: the start and end date, total dose, dose per fraction, number of fractions, and location of treated lesion.

¹⁴Survival assessment may be carried out via chart review or phone call only.

¹⁵A window of \pm 14 days around the standard time point every 3 months is allowed as necessary

¹⁶A minimum of one scan every 4 months is required, however, scans may be completed at more frequent intervals as clinically indicated.

¹⁷Performed in coordination with imaging studies, at baseline prior to treatment, and thereafter only for a change in extracranial response on follow-up imaging. The blood will be drawn within 30 days of any imaging study showing a change in extracranial response status.

¹⁸Optional rebiopsy of an accessible non-irradiated tumor may be obtained at the treating physicians' discretion if it is deemed clinically warranted and safe to perform, for diagnostic purpose in order to confirm progression of disease and underlying histopathology. If indicated, it should be carried out within 30 days of the confirmatory imaging study showing disease progression, and prior to initiating any further systemic therapy.

¹⁹AEs and SAEs will be collected on a continuous basis starting with the first cycle of immune therapy. Both AEs and SAEs will be collected up until 30 days after the last dose of immune therapy or until the patient begins a new cancer-directed therapy, or death, whichever comes first.

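### The response-change blood sample may be drawn after new radiation has begun, which can happen after stable disease or progression but not after response, so a biomarker comparison using it can be confounded

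*Combined protocol and SAP*

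**What the plan says.** The only timing rule for the response-change sample is footnote 17 of section 10.2: "The blood will be drawn within 30 days of any imaging study showing a change in extracranial response status". Sections 9.1.3, 9.2.3 and 9.3.3 say only that blood is taken at baseline and when response status changes. Section 1.3 and the synopsis add a sample at the first reimaging study.

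Section 5.3 makes treatment after the scan depend on its result:

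- Response: "Patients with a partial or complete response per irRC criteria will be observed without any further radiation therapy until progression".
- Stable disease: another course, for which "Day 1 of radiation should be on Day 1 of the next cycle of immune therapy".
- Progression: "Patients with progressive disease at any time per irRC criteria will undergo a final course of radiation therapy". It is given with a final immune therapy cycle, or alone "within 6 weeks after discontinuation of immune therapy but before an alternative systemic therapy is initiated".

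Section 2.4 holds that radiation schedules differ in their immune action "through their differential effects on the up- and down-regulation of CD8 T-cells, Treg and MDSC cells"; CD8 and Treg cells are among the markers measured. Footnote 18 gives the optional rebiopsy a 30-day limit too, but adds "and prior to initiating any further systemic therapy". Footnote 17 has no such condition.

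Section 13.2 powers a two-sample t-test of biomarkers between responders and non-responders. Sections 9.1.2 and 9.2.2 put the same data into the logistic model. None of these sections says which sample is used, or how treatment given between scan and draw is handled.

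**The concern.** If radiation alters circulating immune cells, cytokines or chemokines, the interval between scan and draw matters most when radiation falls inside it. Under section 5.3 that can happen after stable disease or progression, but not after response. The contamination is therefore tied to the grouping variable. A difference between the groups could be an effect of the new course rather than a correlate of response, or a real difference could be hidden. The correlative objective and the predictive logistic model both depend on these data. Blood drawn after radiation has started cannot be replaced later.

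**Working it through.** **1. Can the next course fall inside the window?** Section 5.2 gives cycles of 14, 21 or 28 days, and sections 3.3 and 5.1.1 give courses lasting 3 to 21 days. The longest cycle (28 days) is shorter than 30 days, so the next Day 1 can precede a permitted draw. A course can also finish first: one starting 9 days after the scan and lasting 21 days ends at day 9 + 21 = 30.

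For progression, the exposure depends on which scan triggers the draw. Section 3.3 defines progression by two scans at least 4 weeks apart; section 11.1.1 only recommends the confirmatory scan.

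- Draw keyed to the first scan, and confirmation done: 30 − 28 = at most 2 days of the window follow confirmed progression.
- Draw keyed to the confirmatory scan, or no confirmation done: up to 30 days are exposed.

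Footnote 17 does not say which scan is meant.

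**2. The plan's own figure.** Section 13.2 gives N = 33, a response rate of at least 35% (0.35 × 33 = 11.55, about 12 versus 21), a 50% difference, CV 0.45, and a two-sided 5% test. Taking the SD as 0.45 of the mean in both groups:

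- noncentrality = (0.50/0.45) × √(12 × 21/33) = 1.111 × 2.763 = 3.07, with 31 degrees of freedom and critical value 2.04;
- power = 84.5% (83.0% for 11 versus 22).

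The stated 80% or more is reproduced. The draw window introduces a possible bias; it is not an arithmetic error.

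**3. Illustrative size of the bias.** Assume no true difference, and let a share f of the 21 non-responder samples shift by s, a fraction of the mean. The spurious mean difference is f × s (for example 0.5 × 0.30 = 0.15). Every f and s here is an assumption; the documents give neither. Because only some samples shift, the non-responder variance also grows by s² × f × (1 − f), so the mixture was simulated:

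| Share affected | Shift 20% | Shift 30% | Shift 50% |
|---|---|---|---|
| One half | 8.9% | 13.5% | 26.7% |
| One quarter | 5.8% | 6.9% | 9.8% |

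These are rejection rates against a nominal 5%. A formula that moves the group mean and ignores the added variance gives 9.1%, 14.5% and 31.9% for one half, and 6.0%, 7.3% and 11.5% for one quarter, which is too high.

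The bias can also mask a signal. If responders are truly 50% higher and half of the non-responder samples are raised by 25%, power falls from 84.5% to 59.1%.

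**4. What excluding late samples would cost.** The step 2 formula with 12 responders and fewer non-responder samples gives 84.5% with 21, 80.0% with 16, 73.9% with 12 and 69.5% with 10.

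**The case against.** Several stronger readings are tempting, and the documents do not support them.

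- *Progressors' samples will reflect a new drug.* Section 5.3 places the final radiation course before any alternative systemic therapy. The calendar marks no research blood in the column for follow-up after progression or a switch. A draw after a switch is not forbidden, but it is not planned.
- *Samples at response are free of new treatment.* They are free only of new radiation. Checkpoint inhibitor infusions continue and can fall within the 30 days.
- *The comparison is confounded.* It can be. The baseline sample precedes the first immune therapy dose, and if that is the sample analysed, footnote 17 has no effect on the comparison.
- *Footnote 18 shows the blood sample was overlooked.* The rebiopsy is marked in the post-progression column and so needs its condition, whereas the blood sample is not. Footnote 18 is also silent on radiation. The contrast is suggestive, no more.

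Other points on that side also stand. Thirty days is an outer limit, and section 9 points to a draw at the time of the change. Footnote 17 draws follow-up blood only on a change, so a persistently stable patient may have no sample except the first-reimaging one in section 1.3; 21 non-responder samples may be too many to assume. The statement in section 2.4 is preclinical, compares short with conventional courses, and does not address circulating levels. Radiation and infusion dates (footnotes 12 and 13) and the collection date and time (sections 9.1.4, 9.2.4 and 9.3.4) are recorded, so overlap can be identified.

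None of this supplies the missing order. No rule puts the draw before the next fraction, and no analysis rule uses the recorded dates.

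**Conclusion.** The point holds as a gap in the timing rule. A site following footnote 17 and section 5.3 exactly can collect samples after stable disease or progression that already reflect new radiation, while samples taken at response cannot. Any responder versus non-responder comparison that uses these post-baseline samples can therefore be confounded.

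The size is unknown. On the assumed inputs, the false-positive rate ranges from about 6% (a quarter of samples shifted by 20%) to about 27% (half shifted by 50%). If few draws are late, or the shift is small, the rate stays near 5%. The conclusion rests on a post-baseline sample entering the analysis, on draws being made late enough to overlap a course, and on radiation moving the markers. Baseline samples, the stated biomarker power calculation and the primary response-rate analysis are unaffected. This is a cheap improvement to a correlative endpoint.

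**What to change.** Amend footnote 17 and sections 9.1.3, 9.2.3 and 9.3.3 to:

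1. name the triggering scan, first or confirmatory;
2. require the research draw within 30 days of that scan and before the first fraction of any radiation course, or any new systemic therapy, started in response to it, with treatment timing left as it is.

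In sections 13.2 and 13.3, state which sample (baseline, first reimaging or response change) enters the t-test and the logistic model. Use the dates already recorded to flag any sample drawn after new treatment, and add a sensitivity analysis that leaves flagged samples out.

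The draw order should be the main remedy. Relying on exclusion would be costly: losing 5 of 21 non-responder samples brings power to 80.0%, and losing 11 brings it to 69.5%. The change needs no extra procedure. Its cost is a tighter draw window, with some samples missed or flagged.

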1.2. Secondary Objective(s)

To determine 1-year progression-free survival (PFS); 1-year overall survival (OS); safety/toxicity using CTCAE v4.0 until 30 days after the last dose of immune therapy or until the patient begins a new cancer-directed therapy, or death, whichever comes first; quality of life using FACT-L and FACIT Fatigue Scale at 3 month intervals until the time of systemic disease progression. In order to determine factors predictive of response to therapy, we will correlate the presence of response with radiotherapy variables (biologic effective dose, number of fractions, duration of radiotherapy, sequence of radiation and immune therapy), tumor variables (irradiated tumor site, size, histology, PD-L1 status, local response, extent of prior chemotherapy use), and patient variables (age, smoking status, and biologic correlates).

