3.3. Expected Duration of Treatment and Subject Participation

Each course of radiation therapy will be 3-5 fractions delivered over 3-21 days. The first course of radiation will be initiated at any time point between the date of cycle 1 of immune therapy through the date of cycle 2 of immune therapy. The duration of immune therapy administration and the number of courses of radiation therapy that a subject receives will be dependent upon the subject's response to prior treatment. There is no specific maximum number of cycles of immune therapy if a patient continues to respond to treatment, or courses of radiation therapy if a patient has persistent stable disease on imaging. Progressive disease will be defined per irRC criteria as assessed by two imaging studies \geq 4 weeks apart. Because abscopal responses have been reported even when the radiation is given after the immune therapy was completed, a final course of radiation therapy will be offered to patients at the time of progressive disease on imaging.³⁸⁻³⁹ Subsequent therapy decisions will be at the discretion of the treating physicians, including the option of continuing the immune therapy past progression if clinically indicated.

The radiation therapy or immune therapy may be cancelled or discontinued at any point if no longer medically advisable due to intercurrent illness, toxicity/adverse event, decline in performance status, pregnancy, the best interests of the patient, or death. Subjects may also withdraw consent from treatment (partial consent) or from the study (full consent).

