7.2. Adverse Event Evaluation

The investigator or designee is responsible for ensuring that all adverse events (both serious and non-serious) observed by the clinical team or reported by the subject which occur after the subject has started immune therapy are fully recorded in the subject’s medical records. Source documentation must be available to support all adverse events. A laboratory test abnormality considered clinically relevant (e.g., causing the subject to withdraw from the study, requiring treatment or causing apparent clinical manifestations, result in a delay or dose modification of study treatment, or judged relevant by the investigator), should be reported as an adverse event.

The investigator or sub-investigator (treating physician if applicable) will provide the following for all adverse events (both serious and non-serious):

- Event term (as per CTCAE version 4.0)
- Description of the event

- Date of onset and resolution
- **Expectedness of the toxicity**
- **Grade of toxicity**
- **Attribution of relatedness to the investigational agent- (this must be assigned by an investigator, sub-investigator, or treating physician)**
- Action taken as a result of the event, including but not limited to; no changes, dose interrupted, reduced, discontinued, etc. or action taken with regard to the event, i.e. no action, received con-med or other intervention, etc.
- Outcome of event

The most common adverse event from the short courses of focal radiation therapy used in this study will be fatigue. This may be accompanied by decreased appetite, changes in taste, or weight loss. Since radiation is a focal, localized treatment to a specific targeted tumor, the likelihood of all other side effects is dependent on the part of the body that is treated, as described in the table below. Unknown side effects may also arise due to the combination of radiation therapy and immunotherapy in this study.

	Acute/Short-Term/Temporary	Chronic/Long-Term/Permanent
Skin	redness, dryness, darkening, itching, peeling, tenderness, hair loss	thickening, firmness, discoloration, hair loss
Bone	decreased blood counts	fracture, pain
Nerves	electrical sensation	pain, loss of strength, numbness, tingling, paralysis
Lymphatics	Swelling	lymphedema
Brain	fatigue, brain swelling, headaches, nausea, vomiting, dizziness, drowsiness, altered taste or smell	loss of strength, numbness, tingling, paralysis

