7.3. Adverse Event Reporting Procedures

All patients will be evaluable for toxicity from the time of their first treatment with immune therapy. It is the responsibility of all investigators to assess AEs during the subject's participation in the study. Subjects will be followed for **30** days after treatment has stopped or until an alternative systemic therapy has been started or until death, whichever comes first. Each AE should be followed until resolution, stabilization, or until it has been determined that the study treatment or participation is not the cause.

Adverse events that occur after the subject has started immune therapy must be documented in the study database/case report forms (OnCore or other PRMC approved database), subject's medical records, and as required per additional institutional standards. Source documentation must be available to support all reported adverse events.

A laboratory test abnormality considered clinically relevant (e.g., causing the subject to withdraw from the study), requiring treatment or causing apparent clinical manifestations, or judged relevant by the investigator, should be reported as an adverse event.

This protocol will use the NCI Common Terminology Criteria for Adverse Events (CTCAE) version 4.0 available at <http://ctep.cancer.gov> for adverse event reporting.

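### Adverse-event collection closes 30 days after the last immune-therapy dose, but a protocol radiation course may be given up to 42 days after immune therapy stops

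*Combined protocol and SAP*

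**What the plan says.** Two places give the same end to adverse-event (AE) collection. Section 1.2 defines the toxicity endpoint as running "until 30 days after the last dose of immune therapy or until the patient begins a new cancer-directed therapy", or death, whichever is first. Footnote 19 of section 10.2 repeats this: "Both AEs and SAEs will be collected up until 30 days after the last dose of immune therapy". Neither mentions radiation.

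Section 5.3 gives patients with progressive disease a final radiation course, either with a last cycle of immune therapy or as "stand-alone treatment within 6 weeks after discontinuation of immune therapy but before an alternative systemic therapy is initiated". Section 3.3 sets the length: "Each course of radiation therapy will be 3-5 fractions delivered over 3-21 days". Section 5.2 also says a final course should be offered after any permanent discontinuation of the immune agent, before the switch to another therapy, and states no 6-week limit there.

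Other sections state AE rules in different terms:

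- Section 7.2 covers AEs "which occur after the subject has started immune therapy are fully recorded", with no end date in that sentence.
- Section 7.3 says "Adverse events that occur after the subject has started immune therapy must be documented in the study database/case report forms", again with no end date. It also follows subjects for 30 "days after treatment has stopped or until an alternative systemic therapy has been started", or until death. *Treatment* is not defined.
- Section 3.4 ends general follow-up 30 days after progression or alternate systemic therapy. It also follows AEs that arise after study treatment stops until they resolve or stabilise, and keeps possibly related serious adverse events (SAEs) reportable after the study period.
- Sections 7.4 to 7.6 route SAEs to OnCore and the toxicity committee without a time limit.

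**The concern.** Section 6.2 says the immune therapy is not the experimental component, yet the AE clock runs from immune therapy and ignores radiation. A radiation course that the protocol itself provides for can start after collection has closed.

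This is foreseeable. Section 6.2 calls for permanent discontinuation after grade 3 or 4 immune toxicity, and section 5.2 then offers a final course. For progression, section 11.2 requires two observations at least 4 weeks apart. If dosing stops at the first scan, confirmation alone uses about 28 of the 30 days. Dosing may also continue past progression (section 3.3), so this is one route among several.

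Safety of the combination is part of the overall objective (section 1), and toxicity is a secondary endpoint reported as AE frequency tables (section 13.3). Under section 1.2 and footnote 19, events after a late stand-alone course are left out of those tables. Under section 7.3, read to include radiation, they are counted. Two people following the protocol could tabulate different events for the same patient, and the narrower rule omits toxicity of the treatment under study.

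**Working it through.** The plan gives no figure to reproduce, so this is a comparison of dates.

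**Inputs**

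- Window closes on day 30 after the last immune-therapy dose (section 1.2; footnote 19).
- Stand-alone course within 6 × 7 = 42 days of discontinuation (section 5.3).
- Course length L = 3 to 21 days (section 3.3).
- Assumption: day 0 is the last dose, and discontinuation is dated to it. The protocol does not define the discontinuation date.

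**Formulas**

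For a course starting on day s, the last fraction falls on day e = s + L − 1. The course is wholly outside the window if s ≥ 31. Post-radiation days inside the window are max(0, 30 − e) = max(0, 31 − s − L).

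**Reading A: 6 weeks limits the start (s ≤ 42)**

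- Starts on days 31 to 42 are wholly outside: 12 start days, for every L.
- At s = 42, e = 42 + 3 − 1 = 44 for L = 3, and 42 + 21 − 1 = 62 for L = 21.
- The course then ends 44 − 30 = 14 to 62 − 30 = 32 days after closure.

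**Reading B: the course must finish by day 42 (s ≤ 43 − L)**

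- L = 3: s ≤ 40, so starts on days 31 to 40 are wholly outside (10 start days).
- L = 12: s ≤ 31, so only a start on day 31 is wholly outside.
- L = 13 to 21: s ≤ 30, so none is wholly outside, but a course can run up to 42 − 30 = 12 days past closure.

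**Post-radiation coverage, either reading**

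| Course length | Start on day 1 | Coverage reaches 0 from start day |
|---|---|---|
| 3 days | 31 − 1 − 3 = 27 days | 28 |
| 21 days | 31 − 1 − 21 = 9 days | 10 |

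**Sensitivity to the discontinuation date**

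If discontinuation were dated to the next scheduled dose, the 14-, 21- and 28-day cycles in section 5.2 would move the 6-week limit to day 14 + 42 = 56, 21 + 42 = 63 or 28 + 42 = 70. Day 0 is therefore the narrow case.

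**Against section 7.3**

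If *treatment* includes radiation, a course ending on day 62 is covered to day 62 + 30 = 92. Under footnote 19 the same patient's collection ended on day 30.

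**Calendar**

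The AE/SAE row in section 10.2 is blank in the post-progression column. That fits footnote 1, which places the last formal assessment at progression, and it does not cancel the continuous collection in footnote 19. Still, no AE check is named after the final course, and the radiation record in section 10.1.2 lists dates, dose and fractions only.

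**The case against.** The strongest reply is that much of the other text complements footnote 19. Section 7.2 is a source-record rule with the same start and no competing end date. Section 3.4 concerns general follow-up and the follow-up of individual events. Only section 7.3 gives a rival 30-day anchor, and since sections 3.3 and 5 describe radiation as treatment, 7.3 probably covers the late course already. SAEs are largely protected by sections 3.4 and 7.4 to 7.6. The endpoint window is explicit in section 1.2, and section 13.3 sets no other, so an analyst could simply apply it. The affected group may be small, because the final course can be given with a last immune-therapy cycle. Section 5.3 also requires reimaging after further radiation. Finally, no passage promises 30 days of collection after radiation unless 7.3 is read that way.

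Much of this stands. The section 7.2 strand is thin and the point does not need it. The exposure is mainly non-serious events, plus any event left out of the section 1.2 endpoint. The 27- and 9-day figures describe coverage; they do not show a breach of a stated promise. It would also be strained, though nothing rules it out, to treat protocol radiation as a *new cancer-directed therapy* that closes collection.

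The central point remains. Section 7.3 neither defines *treatment* nor overrides footnote 19. If section 1.2 is applied as the endpoint rule, the result is settled, but it omits toxicity from a protocol radiation course. Reimaging, with timing left to the physicians, is not an AE assessment.

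**Conclusion.** The concern holds: the collection rule in section 1.2 and footnote 19 is wrong as written for stand-alone final courses. With discontinuation dated to the last dose, there are 12 start days (reading A) or up to 10 (reading B) on which a permitted course falls wholly outside collection. No stand-alone course begun on day 1 or later gets 30 days of post-radiation collection. A later discontinuation date would allow still later courses.

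Courses given while immune therapy continues are inside the window. The number of patients with late stand-alone courses cannot be derived from the documents. The primary endpoint and sample size are unaffected. This should be fixed because it bears on the secondary safety endpoint for the experimental component.

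**What to change.** Reconcile section 1.2 and footnote 19 with sections 3.4, 5.3, 7.2 and 7.3 to one window. AEs and SAEs are collected until 30 days after the later of the last immune-therapy dose and the last fraction of protocol radiation, ending earlier at death or at a new non-protocol cancer therapy. Then:

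- use one term for that therapy limit in place of the two now in use (*new cancer-directed therapy* in 1.2 and footnote 19, *alternative systemic therapy* in 7.3), and state that protocol radiation does not trigger it;
- define *treatment* in section 7.3 as immune therapy plus protocol radiation;
- mark an AE/SAE check, by contact or chart review, after the final course in the section 10.2 calendar.

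The 30 days keeps the length the protocol already uses and changes only the anchor. Radiation timing is unchanged. The cost is amendment wording and about one extra contact or chart review for each patient who receives a late final course, with no extra patients and no change to treatment.
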